9.4.7 SUB-GROUP ANALYSES

Sub-group analyses will not be used in this study, as the sample size is too small to conduct analyses based on age, sex, race/ethnicity or other demographic characteristic(s).

9.4.8 EXPLORATORY ANALYSES

We have previously described two exploratory outcomes:

Lupus Brain		Version 1.8
Protocol		4 March 2022

1. To investigate the outlasting effects, if any, of tACS on brain activity and clinical measures.
2. To investigate whether tACS increases cognitive control signals during cognitive tasks that probe sustained attention, selective attention, and working memory.

For (1), we will follow the same analyses as described in 9.4.2 through the two follow-up visits. For (2), we will calculate correlations between frontal midline alpha and theta activity (as measured from EEG recordings) and accuracy at cognitive tasks (reaction time for attention tasks, accuracy for working memory task). The resulting data may be used as covariates (if deemed appropriate) or may just be used as preliminary data for future studies.

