3 OBJECTIVES AND OUTCOME MEASURES

OBJECTIVES	OUTCOME MEASURES	JUSTIFICATION
Primary		
To investigate the physiological changes in patients with systemic lupus erythematosus over the course of a 5-day, 40-minute stimulation protocol, specifically changes in alpha oscillation power from resting-state EEG recordings from baseline (Day 1) to Day 5 of stimulation.	Resting state EEG recordings taken on Day 1 and Day 5 of stimulation.	The protocol is for a 5-day intervention. The primary objective is focused on looking at the change in brain activity over the course of the intervention. Long-term effects (2-week follow-up and 4-week follow-up) will be assessed as exploratory outcomes.
Secondary		
To elucidate the relationship between changes in EEG and changes in pain and depression symptoms, by comparing the changes in symptoms and the change in alpha oscillation power over the course of the intervention (baseline to day 5 of stimulation). The SF-36 will be evaluated at screening and 4-week follow-up.	Correlations between clinical assessments and alpha oscillation power (as measured by resting state EEG recordings) from Day 1 and Day 5 of stimulation.	The objective is to target engagement (i.e., if the stimulation paradigm changes brain activity); the secondary objective is to determine if this engagement resulted in behavioral changes.
Exploratory		
To investigate the outlasting effects, if any, of tACS on brain activity and clinical assessments.	Resting state EEG recordings taken on 2-week and 4-week follow up visits.	The objective is to explore if any changes in brain activity persist as long-term effects. Long-term effects are detected at the 2-week and 4-week follow ups.
To investigate whether tACS increases cognitive control signals during cognitive tasks that probe sustained attention, selective attention, and working memory.	Correlations between frontal midline alpha and theta activity (as measured from EEG recordings on D1, D5, 2-week, and 4-week follow up visits) and accuracy at cognitive	We hypothesize that tACS will improve cognitive control. In particular, we hypothesize that alpha frequency tACS will improve performance the most for tasks that require attention (sustained attention and selective attention tasks),

Lupus Brain		Version 1.8
Protocol		4 March 2022

OBJECTIVES	OUTCOME MEASURES	JUSTIFICATION

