	tasks (reaction time for attention tasks, accuracy for working memory task).	whereas theta frequency tACS will improve performance the most for the working memory task.

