8.2.2 COGNITION

1. A battery of cognitive assessments, designed to assess the cognitive deficits common in lupus, will be administered at baseline (day 1 of stimulation), day 5 of stimulation, and at both follow-up visits. This battery will be used to assess any changes in cognition following the intervention and will also be used to determine if tACS has any negative effect on cognitive abilities.

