9.1.2 SECONDARY EFFICACY HYPOTHESIS

Null hypothesis: There is no relationship between the changes in alpha frequency power and the changes in depression (using the IDAS and HDRS), pain (using the comparative pain scale and pain catastrophizing scale), and cognition (using the sustained attention task, selective attention task, working memory task, and FSCMC).

Alternate hypothesis: There is a relationship between the changes in alpha frequency power and the changes in depression (using the IDAS and HDRS), pain (using the comparative pain scale and pain catastrophizing scale), or cognition (using the sustained attention task, selective attention task, and working memory task, and FSCMC).

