9.4.3 ANALYSIS OF THE SECONDARY OUTCOME MEASURE(S)

Using the EEG results described in 9.4.2, mean dB change from baseline will be correlated with normalized change in HDRS* as well as the other described measures. Correlations will be assessed using Pearson's r and data will be plotted against the best fit line to visualize the results.

*HDRS normalization:

$$\frac{[\text{HDRS score at Visit \#}] - [\text{HDRS score at baseline}]}{[\text{HDRS score at baseline}]}$$

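### No final between-arm analysis of task EEG, task performance or the cognitive battery is specified, although the protocol asks whether tACS improves or harms cognition

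*Combined protocol and SAP*

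**What the plan says.** **Questions posed.** Section 3 states the exploratory aim as "To investigate whether tACS increases cognitive control signals during cognitive tasks that probe sustained attention, selective attention, and working memory". Its justification column predicts a different best arm by task type: "we hypothesize that alpha frequency tACS will improve performance the most for tasks that require attention", "whereas theta frequency tACS will improve performance the most for the working memory task". Section 8.2.2 gives the cognitive battery a safety purpose as well: it "will also be used to determine if tACS has any negative effect on cognitive abilities".

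**Analyses given.**
- Section 9.4.8, item (2): "we will calculate correlations between frontal midline alpha and theta activity (as measured from EEG recordings) and accuracy at cognitive tasks", with reaction time used for the attention tasks and accuracy for working memory. On what happens next: "The resulting data may be used as covariates (if deemed appropriate) or may just be used as preliminary data for future studies".
- Section 9.1.2 puts cognition among the secondary hypotheses, under a null that begins "There is no relationship between the changes in alpha frequency power and the changes in depression". Section 9.4.3 tests it with Pearson's r: "mean dB change from baseline will be correlated with normalized change in HDRS* as well as the other described measures".
- Section 9.4.2 has a treatment-by-session mixed model, specified for resting-state alpha power. Section 9.4.8 carries it over to item (1), the lasting effects on brain activity and clinical measures. Cognition is item (2), with its own method.
- Section 9.4.4 (safety) lists the suicide questionnaire, C-SSRS, adverse effects questionnaire and YMRS. It does not list the battery or the tasks.
- Section 9.4.6 sends blinded descriptive summaries, including cognitive scores, to the DSMB every 6 months. If there is reason to look further, the DSMB can receive participant numbers grouped by coded arm.

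**The concern.** Whether tACS raises a signal, or helps or harms performance, is a question about differences between randomized arms. A correlation between EEG and performance is a different quantity. It can be strong when stimulation does nothing, because people with more frontal theta may simply perform better. It can be near zero when stimulation shifts performance by some other route.

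The tasks are repeated at Day 1, Day 5 and both follow-up visits, so change within a person mixes practice with treatment. The sham arm is what separates the two, and no specified final analysis of the tasks or battery uses it. Followed as written, the plan yields no alpha-sham, theta-sham or alpha-theta estimate for any task signal, task score or battery score. Any such comparison made later would be post hoc, chosen from several tasks, EEG measures and visits.

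**Working it through.** **1. The plan's own figure.** No power or precision figure is given for cognition. The only one (Section 9.2) concerns the EEG alpha difference: difference 2, SD 1.2, alpha 0.05 (taken as two-sided), 20 per group, more than 80% power. Recomputed, the power is 99.95% (99.92% by the noncentral t), so the statement is true as an inequality. This point does not rest on it.

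**2. Question against method.**

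| Question | Quantity needed | Specified analysis | Treatment term? |
|---|---|---|---|
| Does tACS increase task signals? (Section 3) | Arm difference in task alpha and theta power | 9.4.8(2) correlation | No |
| Alpha best for attention, theta best for memory? (Section 3) | Alpha-theta and active-sham differences in performance | 9.4.8(2) correlation; 9.4.3 Pearson's r | No |
| Does tACS harm cognition? (8.2.2) | Active-sham difference in battery scores | None in 9.4.4; DSMB review in 9.4.6 | Not in a final analysis |

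**3. Why a correlation cannot stand in.** Write a person's change in performance as practice + arm effect + error. The difference in mean change between an active arm and sham removes practice and leaves the arm effect. Pearson's r within an arm does not change when a constant is added to everyone's score, so it contains neither practice nor the arm effect. Pooled over arms, r moves only to the extent that arm shifts in EEG and in performance happen to line up.

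**4. Illustration.** Assumptions: three arms of 15 (the 45 evaluable participants of Section 9.3, split equally), normal data with unit SD within arm, r pooled over arms because the plan names no arm term, one-way ANOVA as the comparison by arm, 5,000 simulated trials per row.

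| Scenario (no EEG effect in any row) | Mean pooled r | r significant | ANOVA by arm significant |
|---|---|---|---|
| No arm effect, within-arm r = 0.5 | 0.49 | 95.0% | 4.7% |
| 1 SD worsening in both active arms, within-arm r = 0 | 0.00 | 5.1% | 78.7% |
| 1 SD worsening in both active arms, within-arm r = 0.5 | 0.45 | 89.3% | 77.4% |

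Rows 1 and 3 differ by a large harm, yet r goes only from 0.49 to 0.45. Row 2 has the same harm, and r is significant at about its false-positive rate. The 1 SD and the 0.5 are illustrative and do not come from the protocol.

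**5. What an arm comparison could show.** The pairwise standardized difference detectable with 80% power, two-sided 0.05, no multiplicity adjustment, is (1.960 + 0.842) × √(2/n).
- n = 15: 2.802 × 0.365 = 1.02 SD (1.06 by t).
- n = 20: 2.802 × 0.316 = 0.89 SD (0.91 by t).

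The approximate 95% interval half-width at n = 15 is 1.960 × 0.365 = 0.72 SD, before any gain from baseline adjustment. These comparisons would be estimates, not decisive tests.

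**The case against.** **Cognition is not absent from the safety analysis.** A reader might infer that 9.4.4 ignores it. That is not so. The adverse effects questionnaire (Section 6.1.2) has a trouble-concentrating item, given after each of the five sessions, and 9.4.4 plans a comparison between groups for each adverse effect. This stands, but it is one self-reported item about the session. It is not the battery that 8.2.2 assigns to the harm question.

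**The DSMB sees cognitive scores.** It is also too strong to infer that correlations are the only planned use of cognitive data, because 9.4.6 plans descriptive summaries and a possible coded view by arm. The summaries are blinded, so they cannot separate tACS from practice. The view by arm is discretionary and interim, and has no statistic attached.

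**The data could answer the questions.** This is right. Cognition is measured in randomized arms at Day 1, Day 5 and both follow-ups, so the documents do not support saying that the questions are unanswerable. What is missing is the specification.

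**The endpoint matches the analysis.** Section 3 lists correlations as the outcome measure for this objective, so 9.4.8 is faithful to it. That places the mismatch inside Section 3, between the objective with its predictions and the outcome measure.

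**It is exploratory in a pilot.** True, and no primary conclusion depends on it. But Section 9.2 counts the exploratory analyses and the point and interval estimates among the study's most important products. An arm difference in cognition is such an estimate, and none is planned. Low power is a reason to report intervals, not to leave out the contrast.

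**Conclusion.** The point holds as a gap in the analysis plan. No final between-arm analysis is specified for task EEG, task performance or the cognitive battery, although a stated objective, its arm-specific predictions and a stated harm purpose all need one. The planned correlations carry almost no information on benefit or harm by arm, and the planned uses in 9.4.4 and 9.4.6 do not fill the gap. It should be corrected, but it touches an exploratory objective and a safety description, not the primary result.

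Two assumptions matter. First, item (1) of 9.4.8 is read as not covering the tasks; Section 3 ties that item to resting-state EEG and lists cognition separately. Second, 8.2.2 does not say whether its battery is the three EEG tasks of 8.1.1 or something else. The gap exists under either reading, but the protocol should say which is meant. The documents do not support concluding that a cognitive harm in one arm could never be detected in this trial, only that no specified final analysis of the tasks or battery would look for it.

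**What to change.** **Section 9.4.8(2).** Make a between-arm model the main analysis of (a) frontal midline alpha and theta power during each task and (b) reaction time for the attention tasks and accuracy for working memory. Use the post-baseline visits as outcomes, with treatment, session and treatment-by-session terms and the Day 1 value as covariate. The 9.4.2 model should not be copied unchanged: it lists Day 1 as a session level and also uses baseline alpha power as a covariate, so baseline would be both outcome and predictor. Report the Day 5 alpha-sham, theta-sham and alpha-theta differences with confidence intervals, labelled exploratory and without claims of significance. Keep the correlations as descriptive.

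**Section 9.4.4.** Show the same arm differences for the cognitive battery scores, using all randomized participants with post-baseline cognitive data. The per-protocol set of 9.3 would drop anyone who stopped early, including anyone who stopped because of harm. Section 7.1 makes cognitive tasks optional after stopping, so report how many such participants contribute. State what the 8.2.2 battery consists of.

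**Cost.** Plan wording and extra model runs, with no new data. Counting sustained attention as one task, there are 2 bands × 3 tasks + 3 performance measures = 9 outcomes, and 9 × 3 contrasts = 27 Day 5 estimates, with wide intervals at about 15 per arm. Some will look notable by chance, which is why the exploratory label matters.

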10 SUPPORTING DOCUMENTATION AND OPERATIONAL CONSIDERATIONS

10.1 REGULATORY, ETHICAL, AND STUDY OVERSIGHT CONSIDERATIONS

10.1.1 INFORMED CONSENT PROCESS

10.1.1.1 CONSENT/ASSENT AND OTHER INFORMATIONAL DOCUMENTS PROVIDED TO PARTICIPANTS

Informed consent is a process that is initiated prior to the individual's agreeing to participate in the study and continues throughout the individual's study participation. Extensive discussion of risks and possible benefits of tACS will be provided to the participants and their families. Consent forms describing, in detail, the study intervention, device, procedures, and risks are given to the participant and written documentation of informed consent is required prior to the administration of any treatment or assessments used in this study. All consent forms will be IRB-approved and updated with any new information as modifications are made throughout the study.

10.1.1.2 CONSENT PROCEDURES AND DOCUMENTATION

Together, the researcher and potential participants will review the clinical trial in its entirety. At several intervals during the consent review, the researcher will ask the participant questions that will assess the comprehension of the information in the consent. If the participant is unsure or does not know, the researcher will return to that section and more carefully explain the information. Participants must sign the informed consent document prior to any procedures taking place. If needed, the participants will have the opportunity to discuss the study with their surrogates or think about it prior to agreeing to participate. Participants may withdraw consent at any time throughout the course of the trial. A copy of the signed informed consent document will be given to the participants for their records. The rights and welfare of the participants will be protected by emphasizing to them that the quality of their medical care will not be adversely affected if they decline to participate in this study.

10.1.2 STUDY DISCONTINUATION AND CLOSURE

This study may be temporarily suspended or prematurely terminated if there is sufficient reasonable cause. If the study is prematurely terminated or suspended, the Principal Investigator (PI) will promptly inform research staff, study participants, and the IRB and will provide the reason(s) for the termination or suspension. Study participants will be contacted, as applicable, and be informed of changes to study visit schedule.

Circumstances that may warrant termination or suspension include, but are not limited to:

- Determination of unexpected, significant, or unacceptable risk to participants

- Insufficient compliance to protocol requirements
- Data that are not sufficiently complete and/or evaluable

Study may resume once concerns about safety, protocol compliance, and data quality are addressed.

10.1.3 CONFIDENTIALITY AND PRIVACY

Participant confidentiality is strictly held in trust by the participating investigators, their staff, and the research team. This confidentiality is extended to cover testing of biological samples in addition to the clinical information relating to participants.

All data will only be referenced by dummy identifier code. Data will be stored on a password protected computer. A key connecting names and code numbers will be kept in a locked cabinet, accessible only by research personnel. All data will be stored and analyzed on password protected computers, also only accessible by research personnel. Participants will not be identified in any report or publication about this study and there is no risk of deductive disclosure.

10.1.4 FUTURE USE OF STORED SPECIMENS AND DATA

Data collected for this study will be analyzed and stored within the Carolina Center for Neurostimulation/[name] Lab. After the study is completed, the data will be fully de-identified and archived within a locked file cabinet within the Thurston Arthritis Research Center.

Electronic files will be stored on secure UNC servers using either restricted access departmental drives or the REDCap database for this study.

10.1.6 SAFETY OVERSIGHT

Safety oversight will be under the direction of a DSMB under the direction of the NC TraCS Institute. Members of the DSMB will be independent from the study conduct and free of conflict of interest. The DSMB will review AEs every 6 months whereas the PI and/or Co-I will review AEs in real time and make decisions as of participant's continuation of the clinical trial. The PI will review AEs as appropriate with research team and may request additional review by Co-I on a case-by-case basis.

10.1.7 CLINICAL MONITORING

The Purpose of the monitoring plan is to present the Carolina Center for Neurostimulation's approach to monitoring clinical trials. The plan facilitates compliance with good clinical practice.

- (a) The rights and well-being of human subjects are protected.
- (b) The reported trial data are accurate, complete, and verifiable from source documents.
- (c) The conduct of the trial is in compliance with the currently approved protocol/amendment(s), with GCP, and with applicable regulatory requirement(s).

This section identifies key monitoring activities and specifies the data to be reviewed over the course of a clinical trial. This is a single site, investigator initiated, clinical trial so there will be no site monitoring plan in place.

10.1.7.1 THE CAROLINA CENTER FOR NEUROSTIMULATION MONITORING PLAN

The latest version of the approved IRB application for this clinical trial will be followed at all times. This responsibility falls in the hands of the study coordinator and research assistants. If at any time there is a deviation from protocol, the deviation from protocol log will be filled out. All team members will be trained on how and when to use this log. Deviations will be sent to IRB every 4-6 weeks (if necessary).

Data will be verified for completeness following every study session and all data will be entered into REDCap, a secure online database. After a participant has completed his/her participation (full completion through the 3-month follow-up visit or because he/she withdrew prior to completion), data will be re-reviewed for completeness and accuracy. After all data have been collected, data will be re-reviewed by another study coordinator or research assistant who was not involved with the data collection process.

AE and SAE are clearly defined in the Master Protocol. Documents of AE and SAE can be found in the study binder on file within [name]. It is responsibility of the study coordinator to report all events to the PI. Reporting of AEs and SAEs is described within *Section 8.3*.

The PIs and Co-I will have read-only access to the REDCap database. This allows the PIs and Co-I to view reports that provide information on any missing data on an individual participant basis, but does not allow them to add, change or input any data.

10.1.8 QUALITY ASSURANCE AND QUALITY CONTROL

The Carolina Center for Neurostimulation will conduct internal quality management of study conduct, data and biological specimen collection, documentation and completion. Following written Standard Operating Procedures (SOPs), the study coordinators and research assistants will verify that the clinical trial is conducted and data are generated and biological specimens are collected, documented (recorded), and reported in compliance with the protocol, International Conference on Harmonisation Good Clinical Practice (ICH GCP), and applicable regulatory requirements (e.g., Good Laboratory Practices (GLP), Good Manufacturing Practices (GMP)).

10.1.9 DATA HANDLING AND RECORD KEEPING

10.1.9.1 DATA COLLECTION AND MANAGEMENT RESPONSIBILITIES

The study coordinator and research assistants will be responsible for the informed consent process, review for eligibility, questionnaire administration, data entry, device administration, EEG administration, and CRF entries. The study coordinator will be responsible for AE/SAE documentation and reporting, while the PI will be responsible for the AE assessment, review of the AE documentation forms and overview of the research staff.

REDCap will serve as a secure data management tool for this study. Clinical data (including AEs, concomitant medications, and expected adverse reactions data) and clinical laboratory data will be entered into a data capture system provided by REDCap. The data system includes password protection and internal quality checks, such as automatic range checks, to identify data that appear inconsistent, incomplete, or inaccurate. Clinical data will be entered directly from the source documents. The study coordinator and research assistants will have complete access to the REDCap system, while the PIs and Co-I will have read only ability. This will enable the researchers to enter the data and the PIs and Co-I to review.

